5. The supplied tooth bleaching treatment will be used once under supervision at the study site (for first application) and then daily, at home (for a total of 7 days) in accordance with the manufacturer's instructions.
6. Adverse Events (AEs), Serious Adverse Events (SAEs) and medical device incidents collected immediately after subject provides consent to participate in the study by the completion of the Informed Consent Form (ICF). Medical device in this study is the supplied toothbrush.

Property of Haleon- Confidential

May not be used, divulged, published or otherwise disclosed without the consent of Haleon

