Randomized subjects will then complete the tooth sensitivity questionnaire. Subjects will be dispensed their study products (including diary and sundry items) and undertake a supervised brushing with their allocated dentifrice at the clinical site and be scheduled to attend Visit 2 (2 weeks  $\pm$  2 days after Screening/Randomization). Subjects will continue to use their allocated study products (twice-daily) throughout the study and will record this usage in their study diary.

At Visit 2 (2 weeks after Screening/randomization) subjects will undergo a review of their diary and current medications and will then undergo an OST examination. Tooth color and extrinsic tooth stain will be assessed for the same teeth in the same way as at Visit 1. Subjects who fulfil all inclusion/exclusion criteria will continue in the study and will complete the tooth sensitivity questionnaire and the whitening history questionnaire. Subjects will then be dispensed a commercially available 15% peroxide tooth bleaching kit for use at home for 7 days, once per day, as per pack instructions and as detailed in Section 6.1.1.1. Subjects will undergo a supervised tooth brushing (with their study dentifrice) and will floss their teeth and have their first application of the peroxide bleaching at the study site under supervision in accordance with the manufacturer's instructions. Subjects will be instructed in the correct use of the peroxide product for at home use in accordance with the manufacturer's instructions. Subjects will continue to use their assigned dentifrice twice daily and perform their peroxide bleaching daily per instructions, and to record this usage in their supplied diary. Subjects will be scheduled to return to the study site for Visit 3 (after the completion of their 7 -days tooth bleaching period).

[figure not shown]
After the completion of the tooth bleaching period at Visit 3 [7 days after the commencement of tooth bleaching, with an acceptable range of 7-9 days] subjects will return to the clinical site and return their used bleaching kit and undergo a review of their diary and current medications and undergo an OST examination. Tooth color and extrinsic tooth stain will be assessed for the same teeth in the same way as at Visit 1. Subjects will then complete the tooth sensitivity questionnaire and the post-whitening questionnaire and scheduled to return for Visit 4 (12 weeks [ $\pm$ 1 week] after completion of the peroxide tooth bleaching).

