**6.1.1.1 Application of the Peroxide Bleaching**

The peroxide tooth bleaching procedure should be performed at-home (except for the first application which will be performed under supervision at the study site) following manufacturer instructions. Subjects should brush their teeth with the study dentifrice and floss their teeth prior to applying the peroxide gel. Subjects will apply the supplied gel-containing tray to their maxillary teeth per the product instructions. Subjects should apply their peroxide-containing

Property of Haleon- Confidential

May not be used, divulged, published or otherwise disclosed without the consent of Haleon

tray to their maxillary teeth once per day for 15 timed minutes immediately after either their morning or evening tooth brushing with their assigned study dentifrice. Subjects should attempt to perform the tooth bleaching at approximately the same time of day wherever possible. Subjects should perform peroxide bleaching for 7 consecutive days. Should subjects experience gum sensitivity/irritation due to the peroxide, they should apply a thin layer of the supplied petroleum jelly to the affected gum tissue prior to applying the peroxide, taking care not to contact the teeth with the petroleum jelly.

Subjects should note every bleaching event in their diaries to help monitor compliance.

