## 6.7 Compliance

To facilitate subject compliance with product usage requirements:

- First use of their assigned study dentifrice will be carried out under supervision at the study site at the end of the screening visit (Visit 1) and additionally at Visit 2; study staff will demonstrate the correct amount of dentifrice to dispense and how to use the timer to ensure a 2-minute brushing time. Subjects will be provided with a diary at Screening (Visit 1) to record each completed brushing.
- First use of the peroxide tooth bleaching procedure will be carried out under supervision at the study site at Visit 2; study staff will demonstrate the application of the bleaching gel according to manufacturer's instructions. Subjects will be provided with a diary to record each completed tooth bleaching treatment.
- Subjects will attend each study visit with all tubes of dentifrice provided (used and unused) for a visual check of product usage, and with their completed diary for review by study staff. Any suspected over or under use, the number of any missed or additional brushings will be documented as deviations in the CRF; subjects will be re-instructed in the correct use of product and diary completion, as required.
- Subjects will also use the diary to note any issues with their study product, any oral problems, illnesses and new medications/ treatments. Details relevant to safety or efficacy should be reviewed by the investigator (or suitably qualified designee) and transcribed to the CRF, as appropriate; AEs must be documented in the CRF.

The number of any missed or additional applications or doses will be captured as protocol deviations. Subjects will be re-instructed in the correct usage requirements and diary completion as needed.

A record of the number of dentifrice tubes dispensed to and taken by each subject must be maintained and reconciled with study intervention and compliance records. Intervention start and stop dates, including dates for intervention delays and/or dose reductions will also be recorded in the CRF.

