#### **12.3.8.3 Other Therapy**

Number of bleaching occurrences, bleaching compliance (%), number of missed/additional bleaching occurrences will be summarized using descriptive statistics by cumulative visit.

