#### Peroxide bleaching usage

On days where the study staff have indicated you should use your peroxide tooth bleaching kit after either your morning or evening toothbrushing:

- Having brushed your teeth with the supplied toothpaste, floss your teeth. Use the peroxide bleaching gel according to the supplied manufacturer's instructions. You should use the peroxide once-per-day for a total of 7 days. If possible, try to perform your tooth bleaching at roughly the same time each day (morning or evening after your tooth brushing). You should bleach your teeth for 15 minutes (please use the supplied timer). Should you experience any gum soreness or irritation please apply a thin smear of the supplied petroleum jelly to your gums prior to wearing your tray. Try to avoid getting the petroleum jelly in contact with your teeth.
- Record each use of the peroxide bleaching treatment on the diary card. Note any changes to these procedures and reasons for changes (e.g. missed bleaching, only bleached for 10 minutes etc) in the 'Comments' column.

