#### **4.3.2 Bleaching Compliance and Exposure**

Bleaching Compliance will be summarized for mITT Population where number of bleaching, bleaching compliance (%) and missed/additional bleaching occurrence will be summarized using descriptive statistics as separate categories by study product in Table 14.2.1.2 by cumulative visit.

Number of bleaching is defined as: [(date of Visit 3 – date of Visit 2) – number of missing bleaching + number of additional bleaching].

Bleaching compliance (%) is defined as: [100 x (Number of bleaching / Expected number of bleaching)], where expected number of bleaching is defined as: (date of Visit 3 – date of Visit 2).

Bleaching compliance (number of bleaching / bleaching compliance [%] / number of missed bleaching / numbers of additional bleaching) will be listed in Listing 16.2.5.2 for all randomized subjects by study product.

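### The SAP derives the bleaching count and its compliance denominator from the Visit 2 to Visit 3 interval (7 to 9 days), although the course is fixed at 7 applications

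*SAP*

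**What the plan says.** The protocol describes a course of fixed length. Section 6.1.1.1 states "Subjects should perform peroxide bleaching for 7 consecutive days", once per day. Footnote 5 to the Schedule of Activities describes one supervised application at the site "and then daily, at home (for a total of 7 days"). The subject instruction sheet (Appendix 15.2) says "You should use the peroxide once-per-day for a total of 7 days". Section 8.2.1 places the first application at Visit 2. Section 4.1 puts Visit 3 at 7 days after bleaching starts, "with an acceptable range of 7-9 days".

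Section 12.3.8.3 asks for the number of bleachings and percentage compliance, and says that the "number of missed/additional bleaching occurrences will be summarized using descriptive statistics by cumulative visit". It gives no formula.

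SAP 4.3.2 supplies one. The count begins "Number of bleaching is defined as: [(date of Visit 3 – date of Visit 2"), from which missed applications are subtracted and to which additional ones are added. The denominator uses the same interval: "where expected number of bleaching is defined as: (date of Visit 3 – date of Visit 2"). The SAP does not cap the interval at 7, and neither document says how to treat days between the seventh application and a later Visit 3.

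**The concern.** The denominator should be the number of applications the subject was asked to make. That number is fixed, but the SAP lets it vary with the date on which the subject attends Visit 3. An interval of 8 or 9 days is inside the permitted window, so the error affects subjects who kept to the protocol and not only those with visit deviations.

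The same date-difference rule appears in SAP 4.3.1 for brushing. It suits brushing better, because brushing continues through every visit interval. Bleaching stops after 7 days.

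What is at stake is the accuracy of Table 14.2.1.2 and Listing 16.2.5.2. They report how much bleaching each subject received, and bleaching is the common procedure on which the colour-maintenance question rests. They could credit subjects with more applications than the course contains, or show fully adherent subjects as non-adherent.

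**Working it through.** **Inputs**

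- Course: 7 applications, one per day, the first at Visit 2 (Protocol 6.1.1.1, 8.2.1, Schedule of Activities footnote 5, Appendix 15.2).
- D = date of Visit 3 minus date of Visit 2, allowed values 7, 8 and 9 (Protocol 4.1).
- m = applications missed and a = additional applications, both relative to the 7-application course.

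**Formulas**

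- True count: T = 7 − m + a. True compliance: 100 × T / 7.
- SAP count: C = D − (recorded missed) + (recorded additional). SAP compliance: 100 × C / D.

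**Check at D = 7.** The SAP formula reproduces the planned course: no missed applications gives 7 and 100%; one missed gives 6 and 85.7%. There is no error at 7 days.

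**Coding A: missed applications are judged against the 7-application course.** Then C = D − m + a, so the count is too high by D − 7. The error in compliance is 100 × (m − a) × (1/7 − 1/D) percentage points.

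| D | Case | SAP count | True count | SAP % | True % | Error (points) |
|---|---|---|---|---|---|---|
| 8 | none missed | 8 | 7 | 100 | 100 | 0 |
| 8 | one missed | 7 | 6 | 87.5 | 85.7 | +1.8 |
| 8 | two missed | 6 | 5 | 75.0 | 71.4 | +3.6 |
| 8 | one additional | 9 | 8 | 112.5 | 114.3 | −1.8 |
| 9 | none missed | 9 | 7 | 100 | 100 | 0 |
| 9 | one missed | 8 | 6 | 88.9 | 85.7 | +3.2 |
| 9 | two missed | 7 | 5 | 77.8 | 71.4 | +6.3 |
| 9 | one additional | 10 | 8 | 111.1 | 114.3 | −3.2 |

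Compliance is pulled toward 100%: too high when missed exceeds additional, too low when additional exceeds missed.

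**Coding B: the D − 7 idle days are also logged as missed.** Then C = 7 − m + a, so the count is correct, but it is divided by D instead of 7.

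| D | Truly missed | SAP count | True count | SAP % | True % | Error (points) |
|---|---|---|---|---|---|---|
| 8 | 0 | 7 | 7 | 87.5 | 100 | −12.5 |
| 8 | 1 | 6 | 6 | 75.0 | 85.7 | −10.7 |
| 9 | 0 | 7 | 7 | 77.8 | 100 | −22.2 |
| 9 | 1 | 6 | 6 | 66.7 | 85.7 | −19.0 |
| 9 | 2 | 5 | 5 | 55.6 | 71.4 | −15.9 |

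**No coding gives both outputs correctly.** Suppose the SAP count is right, C = T with T > 0. SAP compliance is then T/D, which equals T/7 only when D = 7. Conversely, if the percentage is right, C = T × D / 7, which differs from T when D is 8 or 9. A search at D = 8 and 9 over true counts of 1 to 9, recorded missed from 0 to D and recorded additional from 0 to 3 found no case with both correct.

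**The case against.** The strongest objection concerns weight.

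- **The larger percentages need an unnatural coding.** A day with no prescribed application is not naturally a missed one, and no section tells sites to log it so. Under Coding A an adherent subject always shows 100%, and one missed application shifts compliance by only 1.8 or 3.2 points. This stands: Coding B is a possibility that the documents leave open, not a prediction. The count is still too high by 1 or 2 under Coding A.
- **Nothing planned depends on the figure.** Neither document sets a bleaching-compliance threshold, the primary model has no compliance term, and Table 14.2.1.2 is not marked as topline. Missed and additional applications appear separately in the same table and listing. Protocol 6.7 also records them directly: "The number of any missed or additional applications or doses will be captured as protocol deviations". This stands, and it limits the point to a minor one.
- **Frequency is unknown.** Visit 3 is targeted at 7 days, and the documents do not show how many subjects will come at 8 or 9. This stands, so only per-subject errors can be given.
- **The total might be read as 8.** Protocol 4.1 speaks of 7 days of home use alongside the supervised application. Section 6.1.1.1, footnote 5 and Appendix 15.2 point to 7 in all. Under a fixed total of 8 the date formula would instead fail at intervals of 7 and 9 days. Any fixed total conflicts with a denominator that moves between 7 and 9.

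**Conclusion.** The concern holds and is minor. For intervals of 8 or 9 days, SAP 4.3.2 must misreport the count, the percentage or both. With missed applications judged against the course, the count is overstated by 1 or 2, and compliance is off by up to 6.3 points for a subject with two missed applications at 9 days. With idle days logged as missed, the count is right, but an adherent subject loses 12.5 or 22.2 points.

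These sizes assume a total of 7 applications including the supervised one, and intervals measured as the date difference from Visit 2. The formula and visit window are the same in both arms, so no between-arm bias is claimed. The efficacy analyses are unaffected.

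**What to change.** In SAP 4.3.2:

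- Set the expected number of bleachings to 7, the protocol's own course.
- Define the number of bleachings as 7 − missed + additional, with both terms judged against that course and the supervised Visit 2 application counted once within the 7. A direct count of recorded applications, including the supervised one, is equivalent if home applications are transcribed from the diary.
- State that days after the seventh application and before Visit 3 are not missed.
- Compute compliance as 100 × number / 7.
- Keep the presentation by cumulative visit, as Protocol 12.3.8.3 asks.

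The results then no longer depend on the Visit 3 date: a full course gives 7 and 100%, one missed 6 and 85.7%, two missed 5 and 71.4%, one additional 8 and 114.3%.

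The cost is one formula and one definition. Missed and additional applications are already captured, so the subtraction form needs no new data. The protocol gives no competing formula, so no amendment is needed. If the sponsor reads the home-use wording in Protocol 4.1 as implying a different total, it should be reconciled with Section 6.1.1.1, footnote 5 and Appendix 15.2 before the constant is fixed.

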#### **4.3.3 Prior and Concomitant Medication**

Prior medications/treatments, including prescription and non-prescription drugs, dietary supplements and herbal remedies, taken in the last 28 days and prior to signing the informed consent form, will be documented in the CRF. The prior and concomitant medications will be coded using a validated medication dictionary, World Health Organization Drug Dictionary (WHODD).

Prior medications and prior non-drug treatments will be listed by subject, with drug name, WHODD Drug Synonym, reason, route, dose, unit, frequency, start date and end date both relative to study product start date (Listing 16.2.4.3) for all randomized subjects. Prior medications are defined as those which stopped before the first use of the study product.

Concomitant medications and concomitant non-drug treatments/significant non-drug therapies taken during treatment will be listed similarly (Listing 16.2.4.4) for all randomized subjects with either ongoing or end date displayed.

Concomitant medications that have been taken to alleviate tooth sensitivity/pain will be summarized in Table 14.3.4.2 for all randomized population and will be listed in Listing 16.2.4.5.

Concomitant medications are defined as medications that started or stopped on or after the first use of the study product or are ongoing.

Unknown dates will not be imputed, however if the start or stop date is unknown, then it will be assumed to be concomitant medication unless the partial start date or stop date indicates differently.

### **4.4 Analysis of Efficacy**

The primary population for assessment of efficacy will be the mITT Population.

#### 4.4.1 Primary Efficacy Endpoint

##### 4.4.1.1 Primary Efficacy Endpoint Definition

The primary efficacy variable is mean Vita Bleached guide shade at 24 weeks after tooth bleaching has completed, calculated at the subject level as the average Vita Bleached guide shade over all sites assessed.

Tooth color of the facial surfaces of the six anterior maxillary teeth (tooth numbers 6-11) [Universal tooth numbering system] will be assessed by a single, trained clinical examiner using the VITA Bleached guide 3D-MASTER. The VITA Bleached guide 3D-MASTER uses a value-ranked ordered scale from 1 (the lightest) to 29 (the darkest). The shade level of each tooth surface is scored visually by the clinical examiner with reference to the Bleached guide.

The mean VITA shade score for each subject at each visit is calculated as the mean VITA shade score over all non-missing facial surfaces of six anterior maxillary teeth (tooth numbers 6-11).

Descriptive statistics (n, missing, mean, SD, standard error [SE], median, minimum, and maximum) will be presented for mean VITA shade score at each assessment time point in Table 14.2.2.1.1 for all subjects in the mITT population by study product.

Raw means ( $\pm$  SE) of the mean VITA shade score at each time point will be plotted by study product in Figure 14.2.1.1 for all subjects in the mITT population.

Individual data for mean VITA shade score will be listed for each subject by study product group and visit in Listing 16.2.6.1 for all randomized subjects.

##### 4.4.1.2 Statistical Hypothesis, Model, and Method of Analysis

The primary comparison is between the Test Dentifrice and the Reference Dentifrice in the mITT population. As there is only a single primary objective, no adjustment for multiple comparisons is required.

Study product differences will be tested under the null hypothesis at 24 weeks after tooth bleaching has completed:

- $H_0$ : there is no difference in mean VITA shade score between Test Dentifrice and Reference Dentifrice
- $H_1$ : there is a difference in mean VITA shade score between Test Dentifrice and Reference Dentifrice

Mean VITA Bleached guide shade will be analyzed using a repeated measures ANOVA model with treatment group and study time points (Visit 2 to 5) as factor and treatment group by time point (Visit 2 to 5) as interaction. Subject will be included as a repeated measure with unstructured covariance matrix; the Kenward Rogers degrees of freedom approach will be

applied (Kenward and Roger, 1997). If the model with unstructured covariance matrix does not converge then compound symmetry covariance matrix will be used.

Using the above model, mean differences between Test Dentifrice compared to Reference Dentifrice in Mean VITA shade score will be reported by study product group along with 95% CIs and p-values will be provided in Table 14.2.2.2.1. All p-values presented will be two-sided and assessed at the 5% significance level.

The assumption of normality and homogeneity of variance in repeated measures ANOVA will be investigated. In case of violation of these assumptions, a suitable nonparametric test (Van Elteren Test adjusted for randomization stratification) will be performed, and the results will be provided to support the repeated measures ANOVA results. The non-parametric results will be considered confirmatory under the observation of strong violations of the assumptions.

If there is more than 10% difference in the overall number of subjects between PP and mITT populations, a summary and analysis of the primary efficacy variable will be presented for the PP population in Table 14.2.2.1.2 and Table 14.2.2.2.2 respectively.

